## **Part II Emotion Regulation as the Mechanism Through which the YRI improvements operate**

**Primary Outcomes:** OMPA internalizing, OMPA externalizing

**Primary Predictor:** Group Membership (Control, ENTR-only, YRI+ENTR)

**Hypothesized Mediator:** Emotion Regulation (assessed by DERS)

**Possible Moderators:** Subject gender, age, education level/literacy, session attendance

We hypothesize that the YRI improvements may operate through changes in emotion regulation. This is a proposed mediation model where the primary predictor is group membership, the primary outcome is mental health at 12 months, and the mediator is emotion regulation as measured by the Difficulties in Emotion Regulation (DERS) at six weeks. We will test for the indirect effect of group membership on Mental Health Status using conditional process analysis (Hayes, 2013). The conditional process equations are (if gender modifies the indirect effect for example):

$$DERS(6\ weeks) = B_0 + a * X$$

$$MH(12\ months) = B_0 + cX + b_1 * DERS(6\ weeks) + b_2 * G + b_3 * G * DERS.$$

Where  $X$  is group membership and  $G$  is gender. The coefficient  $a$  quantifies the effect of group membership on emotion regulation and  $b$  quantifies the effect emotion regulation on mental health independent of group membership. The product  $p = a(b_1 + b_3 * G)$  is the *indirect effect* of group membership on Mental Health. We can test for the significance (null hypothesis  $p = 0$ ) via

bootstrapping. A significant (at 0.05) is indication that emotion regulation mediates the relationship between the YRI effects and mental health. For outcomes that are binary we will need to use the KHB method (Breen, Karlson, & Holm, 2013) to rescale the regression coefficients correctly. A strength of this analysis is that group membership, emotion dysregulation and Mental Health are measured at three different time points which is necessary for causal mediation (though not sufficient).

As an alternative we can test for mediation using Structural Equation Modeling (SEM). This approach is more flexible than conditional process analysis and may allow us to use full-information maximum likelihood (FIML) as opposed to multiple imputation. All causal models will be evaluated for the possible effects of unmeasured confounders (VanderWeele & Ding, 2017).

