### Data Analysis Plan for Hypothesis 3a:

*Hypothesis 3(a): Participants who are exposed to YRI will demonstrate greater reduction in mental health and functional problems than participants who do not receive the YRI intervention; emotion regulation (as measured using the Disturbances in Emotion Regulation Scale) will operate as a major mechanism of YRI improvements; high comorbidity will be a treatment modifier.*

**Primary Outcomes** DERS, HSCL, OMPA Externalizing, WHODAS

**Primary Predictors:** Time (baseline, Post-YRI, Post-ENTR, and 12 months and group membership (Control, ENTR, ENTR + YRI).

**Possible Moderators:** Subject gender, age, education level/literacy, session attendance

**Strata Indicators:** Subject ID and Cluster ID. With only three geographic/political districts, an insufficient number to constitute a level in multilevel modeling, the districts will be introduced at the top level (i.e., the clusters) as fixed effects by means of dummy variables to account for any district effects.

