The goal of this analysis is to determine if there are differences among the three groups assigned at randomization (Control, ENTR, and ENTR+YRI). As described above, all analyses will include the aggregated baseline value of the outcome as a control at the cluster level, and furthermore, of any cluster-level potential treatment confounders shown to be imbalanced across the three groups. In particular we will be looking for group differences in the slopes of the primary outcomes over the lifetime of the study. Fixed effects will be time and group membership and their two-way interaction. Each subject will be measured three times—baseline, post-training, and at 12-month follow up—so we have three repeated measures for each subject, and each set of repeated measures is nested within study cluster. Subject- and cluster-specific slopes and intercepts will be modeled as random effects. We can test for the necessity of the subject and cluster specific slopes through likelihood ratio tests. Evidence of a group differential effects will be if the likelihood ratio test for the time by group interaction is significant at the 0.05 level. For pairwise differences we will examine the regression coefficients and base inference on Wald tests. We will estimate the model with Restricted Maximum Likelihood (REML, also MLR) for testing for random effect parameters and Full Maximum Likelihood (FML or MLF) for fixed effects. We will account for attrition by calculating inverse probability weights and/or multiple imputation. All linear modeling assumptions will be verified, both by

evaluating underlying distributions and model residuals. Approaches to the violation of model assumptions or for non-continuous outcomes include use of response transformations, generalized linear mixed effect models or generalized estimating equations.

We now expand the above model to include possible effect modifiers gender, mental health status at baseline. To the model above we will include a three-way interaction between time, gender, and treatment group. Evidence of a moderating effect will be if likelihood ratio test for the three-way interaction term is significant at the 0.05 level.

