As above, we will use cluster-level controls for aggregated levels of the outcome variable in all analyses, because even including the matching techniques employed, the total number of clusters is too small to assume that randomization will achieve balance on all variables. Furthermore, having tested for cluster-level imbalances in all cluster-level variables assessed at baseline, we will adjust models for any cluster-level confounders judged to have likely influence on the outcomes, for example, economic conditions, where significant imbalance was found. Similarly, individual-level confounders will be assessed in models and can be tested for their influence using multivariate generalized linear hypothesis testing to assess the influence of a group of variables or by means of log-likelihood test comparing nested models as described above.

We can use restricted fence methods as an example of variable selections.

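### The mediation tests name no clustering method, no bootstrap unit and no individual baseline adjustment, so false mediation findings can far exceed 5%

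*Combined protocol and SAP*

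**What the plan says.** The Combined protocol and SAP randomises clusters, in matched triads where possible (Analytic procedures for cluster matching prior to randomization). For the repeated-measures model under the Data Analysis Plan for Hypothesis 3a it states: "Subject- and cluster-specific slopes and intercepts will be modeled as random effects".

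Part II of that plan, on emotion regulation as mechanism, changes method: "We will test for the indirect effect of group membership on Mental Health Status using conditional process analysis". The printed equations regress six-week DERS on group, and 12-month mental health on group, DERS, gender and their product. The indirect effect is tested by bootstrapping, and a result significant at 0.05 "is indication that emotion regulation mediates the relationship between the YRI effects and mental health". The plans for Hypotheses 3b and 3c use the same model form. None of the three sections mentions a cluster term, a robust variance or the unit to be resampled, and none includes a youth's own baseline mediator or outcome. The SEM alternative is not described as multilevel. Group has three levels but appears as a single X.

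Three other statements bear on the point:

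- On baseline adjustment, "we will use cluster-level controls for aggregated levels of the outcome variable in all analyses", because "the total number of clusters is too small to assume that randomization will achieve balance on all variables".
- On individual covariates, "Similarly, individual-level confounders will be assessed in models and can be tested for their influence".
- On residual confounding, "All causal models will be evaluated for the possible effects of unmeasured confounders".

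**The concern.** An indirect effect is the product of path a (group to mediator) and path b (mediator to outcome). Each path is exposed to a different error.

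- **Path a.** Group is assigned by cluster. If youths are treated as independent, or resampled one by one, the standard error of a is too small.
- **Path b.** The mediator is not randomised. Youths with worse emotion regulation at entry may also have worse mental health at entry, and both persist. Without individual baselines, that shared starting point appears as an effect of the mediator.

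Either error can give a significant product when there is no mediation. The mechanism claim in Hypothesis 3a and the whole of Hypothesis 3b depend on this test. The printed equations are illustrative, so this is a gap in specification rather than proof of what will be run. An analyst following the text could nevertheless run the invalid version.

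**Working it through.** **Inputs.** From the SAP: the 0.05 threshold, cluster allocation, and the cluster-mean baseline covariate. The threshold is a choice, so there is no derived figure to reproduce. ICC, cluster number and size, N and correlations are not given; all values below are assumptions.

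**Hand check of path a, clustering ignored and no covariate.** Actual alpha = 2 × [1 − Φ(1.96 / √(1 + (m − 1) × ICC))].

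- ICC 0: 5.0%, the nominal level.
- m = 20, ICC 0.05: √(1 + 19 × 0.05) = √1.95 = 1.396; 1.96 / 1.396 = 1.404; alpha = 16.0%.
- m = 20, ICC 0.01, 0.02 and 0.10: 7.2%, 9.5% and 25.0%.

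**Hand check of path b with true b = 0.** With baseline-to-follow-up correlation 0.5 for both variables and baseline mediator–outcome correlation 0.4, the follow-up correlation is 0.5 × 0.5 × 0.4 = 0.10. With 2 × 10 × 25 = 500 youth, z is roughly 0.10 × √500 = 2.2, beyond 1.96 on average although the mediator does nothing.

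**Simulation of the full test.** Two-arm contrast; 10 clusters × 25 or 15 × 20 youth per arm; baseline-to-follow-up correlation 0.5 at both levels; 1,000 trials per setting with 400 percentile-bootstrap resamples. The Monte Carlo SE is about 0.7 points at 5% and at most 1.6. The planned model regresses DERS on X and cluster-mean baseline DERS, and the outcome on X, DERS and cluster-mean baseline outcome.

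- Null 1: a = 0, b = 0.3, baseline mediator–outcome correlation 0.4.
- Null 2: a = 0.3 SD, b = 0, ICC 0.02.

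| Analysis | Null 1, ICC 0.02 / 0.05 / 0.10 | Null 2, baseline correlation 0.3 / 0.4 / 0.5 |
|---|---|---|
| Youths resampled, cluster means only | 6% / 11–15% / 22% | 30–40% / 48–59% / 66–79% |
| Youths resampled, own baselines added | 10–11% / 18–19% / 27–29% | 4–6% |
| Clusters resampled, cluster means only | 7–9% | 36–40% / 52–61% / 68–79% |
| Clusters resampled, own baselines added | 7–10% | 6–8% |
| Multilevel form, own baselines, Monte Carlo interval with small-sample df | 4–6% | 2–5% |

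The planned model with youths resampled gives 3% in null 1 at ICC 0, and 17–21% in null 2 at correlation 0.2. If both paths are null, the test is conservative (0.2–0.4%).

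The last row uses the balanced-design form of the multilevel model: between-cluster regression for a (t with 16 or 26 df), within-cluster regression for b, and 4,000 draws of the product.

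The second row is worse than the first under null 1 for a reason. The cluster-mean covariate removes chance baseline differences between clusters from the estimate, but leaves the individual baseline spread in the bootstrap variance. That cushion explains the 3% at ICC 0, and own baselines take it away.

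**Independent re-computation with other settings.** Null 1 with b = 0.4 and 10 clusters × 20 youth per arm, cluster means only, youths resampled: 3.0%, 5.7%, 10.7% and 21.5% at ICC 0, 0.02, 0.05 and 0.10. Null 2 with 20 × 10 per arm and ICC 0.05: about 4–6% with uncorrelated baselines, 14–42% at correlation 0.3 and 25–75% at 0.5, for baseline-to-follow-up correlations of 0.4 to 0.6. Whole-cluster resampling with own baselines: 4.8–9.3% in null 1 (10 or 20 clusters per arm) and 3.8–5.5% in null 2.

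**The case against.** **The plan is aware of both issues.** It lists Cluster ID among the strata indicators for Hypothesis 3a, names baseline mental health as a possible effect modifier, will assess individual-level confounders, and plans an unmeasured-confounder analysis and FDR control. None of these fills the gap. An identifier is not a variance method, and it is not repeated for 3b or 3c. The modifier belongs to the repeated-measures model. Confounder assessment names neither baseline and leaves inclusion to testing. The unmeasured-confounder analysis does not correct the test, and these confounders are measured. FDR needs valid p-values; the rates above are for a single unadjusted test.

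**The clustering part depends on the ICC.** This stands. With cluster means included and ICC at or below 0.02, the planned model stays at 3–6%. Triad matching, district dummies and dummies for unmatched clusters were not simulated and could lower between-cluster error further. The confounding part does not depend on this.

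**The remedy asks for more than validity needs.** Partly right. Either own baseline in the outcome equation alone brought null 2 to 4–6%, and path a is randomised, so own baselines are not needed there for validity. Including both in both equations does no harm and adds precision and robustness.

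**Hypotheses 3b and 3c were not simulated**, and may involve binary outcomes with KHB rescaling. This stands as a limit on the size, not on the gap.

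**Conclusion.** The concern holds. The mediation sections leave out a clustering method, the resampling unit and individual baseline adjustment, and nothing elsewhere in the plan supplies them.

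Under the assumed designs, clustering raises the false-mediation rate to 11–22% at ICC 0.05–0.10 and matters little at 0.02 or below. Omitting own baselines is the larger risk when YRI does move the mediator: 17–21% at a baseline correlation of 0.2, rising to 66–79% at 0.5. The two failures arise under different nulls, so correcting one leaves the other.

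Confidence in the gap and the direction of error is high. The exact size depends on quantities the documents do not give, and applies to a continuous two-arm contrast of the kind in Hypothesis 3a. This should be fixed before the mediation analyses are run.

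**What to change.** For Hypotheses 3a to 3c, the SAP should state the following:

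1. Fit the mediator and outcome equations as multilevel models with a cluster random effect, or as a two-level SEM if SEM is used.
2. Include each youth's own baseline mediator and baseline outcome in both equations, with the cluster aggregates and district dummies already planned. Make this change together with the first.
3. Enter group as two arm indicators. Report the indirect effect for YRI+ENTR versus ENTR-only, which isolates YRI, together with YRI+ENTR versus Control.
4. Take the interval from a Monte Carlo product with small-sample degrees of freedom for path a. Keep whole-cluster resampling within arm as a sensitivity analysis, since it stayed above 5% in most settings with few clusters.
5. For binary outcomes, say how KHB rescaling combines with the cluster random effect and the interval. That combination was not worked out here.

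**Cost.** SAP wording, some analysis code and wider intervals. No new data should be needed. Baseline is a listed measurement time ("Time (baseline, Post-YRI, Post-ENTR, and 12 months and group membership"), and the required cluster aggregate of each baseline outcome presupposes individual values. For 3b and 3c, the matching variables include income-generating activity and days and hours worked. The SAP should say which baseline item serves for economic self-sufficiency, because it does not equate these with that outcome.

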### **Data Analysis Plan for Hypothesis 3b:**

*Hypothesis 3(b): Improvements in mental health and functioning due to YRI will lead to (mediate) greater employment outcomes and superior economic self-sufficiency over time.*

**Primary Outcome:** Measures of employment and superior economic sufficiency.

**Primary Predictor:** Group membership.

**Mediator:** Mental Health as measured by the HSCL, OMPA; functioning as measured by WHODAS

**Possible Moderators:** Subject gender, age, education level/literacy, session attendance

Similar to Aim 3(a) we will test for mediation using condition process analysis the process equations are similar:

$$MH(12\ months) = B_0 + a * X$$

$$Employment = B_0 + B_0 + cX + b_1 * MH + b_2 * G + b_3 * G * MH$$

The indirect effect of mental health on employment and economic self-sufficiency is quantified by the product  $p = a(b_1 + b_3 * G)$ . We will use a bootstrap test to access significance. Binary outcomes will need to be adjusted using KMB method. The size and direction of effects will be determined by the estimates of the regression coefficients.

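### The gender-moderated mediation equations in Part II let gender act only on the DERS-to-mental-health path, so both genders share one pooled YRI effect on DERS

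*Combined protocol and SAP*

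**What the plan says.** Part II (emotion regulation as mechanism) gives one moderated mediation model, introduced by "The conditional process equations are (if gender modifies the indirect effect for example". With X for group and G for gender, the mediator equation is "DERS(6\ weeks) = B_0 + a * X" and the outcome equation is "MH(12\ months) = B_0 + cX + b_1 * DERS(6\ weeks) + b_2 * G + b_3 * G * DERS". The plan says that a "quantifies the effect of group membership on emotion regulation and" it defines the indirect effect as p = a(b1 + b3×G). It tests p = 0 by bootstrap and states: "A significant (at 0.05) is indication that emotion regulation mediates the relationship between the YRI effects and mental health".

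Three other places bear on this:
- The Hypothesis 3a outcome analysis tests gender as a modifier of the group effect over time: "To the model above we will include a three-way interaction between time, gender, and treatment group". The outcomes listed there are "DERS, HSCL, OMPA Externalizing, WHODAS", so DERS is one of them.
- The Hypothesis 3b plan reuses the form for employment: "Similar to Aim 3(a) we will test for mediation using condition process analysis the process equations are similar".
- The Hypothesis 3c plan says that it will add moderator terms to the 3b model. It writes the indirect effect as (a1 + a3×W)×b, bases the test on a3, counts gender among the dichotomous moderators W, and says that the assumed moderated path runs from group to mediator. Its printed equations contain no a3 term.

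**The concern.** An indirect effect can differ by gender in two ways: YRI may change DERS by different amounts, or DERS may relate to mental health with different slopes. The Part II equations allow only the second. The direct effect is also held equal across genders.

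Moderation of the second path alone is a recognised model, but it needs an equal YRI effect on DERS in both genders. The plan's own three-way test treats that equality as open, and its 3c text assumes moderation on the path that Part II leaves out. At stake is the gender-specific reading. The analysis could report mediation through emotion regulation in a gender whose emotion regulation YRI did not change, understate it in the other, and miss the difference between them.

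**Working it through.** **Inputs.** The equations come from Part II. The documents give no sample size, effect size, SD, ICC or gender split, so every number below is assumed unless it follows from the algebra.

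**Step 1: the plan's formula.** Substituting the DERS equation into the mental health equation gives an indirect effect of a(b1 + b3×G). This matches the stated p, so the formula is correct for the model as printed.

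**Step 2: what a estimates.** Let π be the share with G = 1, and let the YRI effect on DERS be α0 for G = 0 and α1 for G = 1. If gender is balanced across arms, a = (1 − π)α0 + πα1. Both genders receive this average.

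**Step 3: bias when one gender does not respond.** Set α1 = 0. For G = 1 the plan's p is (1 − π)α0(b1 + b3), where the truth is 0. Example: α0 = −0.3 SD, slope 0.3, π = 0.5 gives 0.5 × (−0.3) × 0.3 = −0.045 in both genders; the truth is −0.090 and 0. Over π 0.3 to 0.7, α0 −0.2 to −0.5 and slope 0.2 to 0.5, the spurious effect runs from 0.7 to 0.3 of α0 times the slope, that is from −0.012 (0.3 × −0.2 × 0.2) to −0.175 (0.7 × −0.5 × 0.5).

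**Step 4: the implied gender difference.** Under the printed model it is a×b3. If the DERS-to-mental-health slopes are equal, b3 = 0 and the implied difference is 0, although the true difference is (α1 − α0)×b1.

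**Step 5: how often mediation would be declared.** Take 800 youth, two arms, half women, residual SD 1, slope 0.4 in both genders, and a DERS effect of 0.4 SD in women and 0 in men. Then a = 0.2 and p = 0.2 × 0.4 = 0.08 in both genders, against 0.16 and 0.

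| Setting (assumed) | Mediation declared in men, Part II equations (simulation) |
|---|---|
| Independent youth | about 80% |
| ICC 0.05, 20 per cluster | about 56% |
| ICC 0.05, 50 per cluster | about 37% |

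With the interaction terms added, the rate is about 3 to 10%.

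A normal approximation supports these figures. With independent youth, SE(a) = √(4/800) = 0.0707 and the SE of the slope in men is 1/√400 = 0.05. So SE(p) = √(0.4² × 0.0707² + 0.2² × 0.05²) = 0.030, z = 0.08/0.030 = 2.67, and P(Z > 1.96 − 2.67) is about 76%. Inflating SE(a)² by 1 + 19 × 0.05 = 1.95 or 1 + 49 × 0.05 = 3.45 gives z of 1.96 or 1.50, that is about 50% or 32%. These are a little below the simulated rates, with the same pattern.

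**Step 6: other settings.** A separate simulation used a percentile bootstrap, slope 0.3 and independent youth. In the unaffected gender it gave 22%, 34% and 71% at n = 400 (effects −0.2, −0.3, −0.5 in the other gender), and 33%, 56% and 96% at n = 800. With no effect in either gender the rate was 7.5%, so the excess comes from pooling a. With opposite effects (−0.3 and +0.3, n = 800) the Part II equations detected mediation in 5.5% of trials, against 87.5% with the interaction terms. Pooling can therefore also hide mediation.

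**Step 7: the missing direct-effect interaction.** Omitting group-by-gender from the mental health equation alone biases b3 by only 0.027, for a 0.4 SD gender difference in direct effect and a = 0.3. The important error enters through a.

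**The case against.** The strongest reply is that the equations are labelled an example, that second-path moderation is legitimate, and that gender is only a possible moderator: Hypothesis 3(a) names comorbidity as the modifier, and 3(c) names other characteristics. This stands as a limit on priority. It does not repair the model, which is the only moderated mediation written out for Part II.

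The plan also has partial safeguards. Part II permits SEM, but as an option and with no group-by-gender path. The three-way test could reveal a gender difference in the DERS effect, but no rule carries that result into the mediation model. The check of which path is moderated is optional and belongs to 3c, whose outcomes are economic.

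Four stronger readings are tempting, and the documents do not support them:
- A reader might infer that the employment analysis has the same unaddressed gap, since 3b prints the same form. The 3c text commits to adding terms and includes a3 with a test. What remains there is a mismatch between text and printed equations.
- A reader might infer that the implied gender difference is always zero. That holds only when the two slopes are equal.
- A reader might take 80% as this trial's error rate. It assumes independent youth, 800 participants and exactly no effect in one gender. The trial randomises clusters, and clustering lowers the rate.
- A reader might infer that the overall mediation conclusion is wrong. The plan's decision sentence is not worded gender by gender, and in the example the average indirect effect really is 0.08, so that overall conclusion would be correct.

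**Conclusion.** The concern holds for Part II. The gender-specific indirect effects are valid only under an equal YRI effect on DERS in both genders, which the mediation plan neither states nor tests and which other parts of the plan leave open. If that equality fails, both estimates move toward a common a. In the worked example the error is 0.08 in each gender, in opposite directions. The bias needs no assumption about sample size or clustering. It does need a real gender difference in the effect on DERS and, for a spurious effect in the unaffected gender, a DERS-to-mental-health slope there. The declaration rates of 37% to 80% are illustrative only. Because gender is an illustrative moderator in a secondary mechanism analysis, the priority is modest.

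**What to change.** In Part II, when gender or another baseline moderator is examined, use:
- DERS(6 weeks) = B0 + a1×X + a2×G + a3×X×G
- MH(12 months) = B0 + c1×X + c2×X×G + b1×DERS + b2×G + b3×G×DERS

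Define the indirect effect as (a1 + a3×G)(b1 + b3×G). Judge gender moderation by the bootstrap interval for the difference between the genders' indirect effects. Answer the overall mechanism question from the product in the model without gender interactions. For employment, only make the printed equations in the 3b and 3c plans agree with the 3c text.

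This is a change of SAP wording and needs no new data. The cost is precision in the gender-specific estimates. With independent youth in the example, the SE of the indirect effect rises by about 30% or somewhat more: by the same approximation, from 0.030 to 0.4 × √(4/400) = 0.040 in men. With clustering the rise is smaller; for the a path alone it is about 22% or 13% at an assumed ICC of 0.05 with 20 or 50 per cluster. The overall mediation test is unchanged.

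### The mediation models do not say how three-arm group membership is coded or which contrast represents YRI, so a significant indirect effect can be credited to YRI when ENTR alone produced it

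*Combined protocol and SAP*

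**What the plan says.** Part II of the Hypothesis 3a plan (emotion regulation as mechanism) lists the primary predictor as "Group Membership (Control, ENTR-only, YRI+ENTR", that is, three arms. The mediator equation for six-week DERS contains B0 and a*X. The equation for 12-month mental health contains cX, DERS, gender G and a G-by-DERS term. X is defined only as group membership, and a "quantifies the effect of group membership on emotion regulation". One product, p = a(b1 + b3*G), is called the indirect effect of group membership and is tested by bootstrap. A result significant at 0.05 "is indication that emotion regulation mediates the relationship between the YRI effects and mental health".

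The Hypothesis 3b plan opens with "Improvements in mental health and functioning due to YRI will lead to (mediate) greater employment outcomes". It uses the same a*X and cX terms, with 12-month mental health as mediator, and says: "The indirect effect of mental health on employment and economic self-sufficiency is quantified by the product" p. The Hypothesis 3c plan prints the same two equations for moderators expected to weaken YRI. Its text, however, defines the indirect effect as (a1 + a3*W)*b and tests moderation through a3.

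None of these three sections states a coding for X, a reference arm or a contrast between arms.

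**The concern.** YRI is delivered alongside ENTR, and there is no YRI-without-ENTR arm. A claim about YRI therefore rests on YRI+ENTR against ENTR-only. The Part II rule tests a quantity attached to group membership as a whole and then states the conclusion for YRI. These are different quantities unless X is coded so that a measures the added effect of YRI, and the plan does not say that it is.

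A positive mechanism finding for YRI could therefore come from ENTR. The opposite error is also possible: if ENTR and YRI move the mediator in opposite directions, one coefficient can hide most of the YRI path. Hypothesis 3b is especially exposed, because its outcomes are employment and economic self-sufficiency and ENTR is entrepreneurship training. Leaving the contrast open also means that it could be chosen after the data are seen.

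**Working it through.** The documents give no effect size, SD, arm size or power for the mediation analysis, so there is no figure to reproduce. The check is algebraic. All numbers below are assumptions chosen for illustration.

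**Inputs.** Let e be the effect of ENTR-only versus Control on the mediator, and y the added effect of YRI+ENTR versus ENTR-only. Both are in SD units, positive meaning improvement. The arm means (Control, ENTR-only, YRI+ENTR) are 0, e and e + y. The quantity that a YRI claim needs is y.

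**Least-squares slope on a single X, equal arms.**
- Scores 0/1/2: a = (mean of YRI+ENTR − mean of Control)/2 = (e + y)/2. The ENTR-only mean drops out.
- Scores 0/1/1 (either training versus Control): a = [e + (e + y)]/2 − 0 = e + y/2.
- Scores 0/0/1 (YRI+ENTR versus the rest): a = (e + y) − (0 + e)/2 = e/2 + y.

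| e | y (YRI contrast) | a, 0/1/2 | a, 0/1/1 | a, 0/0/1 |
|---|---|---|---|---|
| 0.3 | 0 | 0.15 | 0.30 | 0.15 |
| 0 | 0.3 | 0.15 | 0.15 | 0.30 |
| 0.3 | 0.3 | 0.30 | 0.45 | 0.45 |
| −0.2 | 0.3 | 0.05 | −0.05 | 0.20 |

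In the first row YRI adds nothing, yet a is nonzero under all three codings. Since p = a(b1 + b3*G), p is then nonzero whenever the mediator affects the outcome. Under 0/1/2 scoring the first two rows cannot be told apart. In the last row 0/1/2 scoring shows 0.05 where the YRI contrast is 0.3.

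**Unequal arms.** With allocation 1:1:2 or 2:1:1, e = 1 and y = 0, the slope across the three codings lies between 0.455 and 1.0 in size. Changing the allocation does not remove the problem.

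**Omnibus reading.** If X stands for a set of indicators and the indirect effect of group is tested as a whole, the null is that e and y are both zero on the mediator path. ENTR alone makes that null false.

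**Illustrative rejection rates.** A simulation set y = 0, with e of 0.2, 0.3 or 0.5 SD and 100, 200 or 400 per arm. It assumed SD 1, b = 0.4, no clustering and no gender term. There were 1,000 replicates per setting, with a Monte Carlo interval for the product at two-sided 0.05. A single X scored 0/1/2 gave a significant indirect effect in 28% to 100% of replicates. The YRI+ENTR versus ENTR-only indirect effect from a two-contrast model was significant in 4.4% to 6.7%.

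**The case against.** The best objection is that X is shorthand. The equations are visibly schematic: they leave out the cluster-level baseline control that the plan requires in all analyses, 3b and 3c print B0 twice, and the 3c equations contain no W, a1 or a3 although the text relies on them. The order in which the arms are listed also varies between sections, which fits poorly with an ordered score. X could mean two indicators, or even a 0/1 contrast of YRI+ENTR with ENTR-only.

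This stands, and it limits the point. A reader might infer that the plan specifies an ordered score, or that YRI cannot be separated from ENTR in this trial. The documents support neither: no coding is given, and the randomised ENTR-only arm makes the separation possible. But shorthand does not close the gap. With two indicators there are two indirect effects, and the plan does not say which one supports the YRI claim. The only abbreviation that 3c declares for its equations concerns moderators.

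Other replies help less:
- Pairwise differences are planned in the Hypothesis 3a section, but for the time-by-group mixed model, and they are not carried into mediation. Dummy variables are described for districts and unmatched clusters, not for arms.
- Six-week DERS might precede ENTR, since the 3a list puts the post-YRI visit before the post-ENTR visit. That would reduce any ENTR contribution in Part II, but no section ties six weeks to either visit. It would not help 3b or 3c, where the mediator is measured at 12 months.
- Hypothesis 3(a) compares YRI recipients with everyone who does not receive YRI, which matches 0/0/1 coding. That contrast still carries e/2 of ENTR effect with equal arms. Taking ENTR-only as the sole reference is therefore a recommendation that goes beyond the wording of the hypothesis.

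**Conclusion.** The concern holds as a gap in specification with a real consequence. In Part II, the coding of X and the contrast that represents YRI are not stated, and the decision rule credits a significant p to YRI. Read literally as one X across three arms, or as an omnibus group test, that rule can attribute to YRI an indirect effect due wholly to ENTR. For 3b and 3c the point is narrower: they reuse the single-X equations for hypotheses about YRI but do not repeat the Part II reading rule, and 3c tests a3 rather than p.

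The values of a (such as 0.15 in both of the first two scenarios) rest on assumed codings, equal arms and chosen effects. The 28% to 100% range rests on further assumptions. A reader might take that range as the false-positive rate of this trial. It is not, because the documents give neither the coding nor the effects needed to estimate one.

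**What to change.** **Part II.** Replace X with two indicators, ENTR-only as reference: X_YRI (1 for YRI+ENTR) and X_C (1 for Control).
- DERS(6 weeks) = B0 + a_YRI*X_YRI + a_C*X_C
- MH(12 months) = B0 + c_YRI*X_YRI + c_C*X_C + b1*DERS + b2*G + b3*G*DERS

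State that the YRI mediation claim rests on a_YRI*(b1 + b3*G). The Control path, with its sign reversed, gives ENTR-only versus Control and can be reported separately. If the sponsor also wants the broader comparison in Hypothesis 3(a), name it as a separate contrast and say that it includes part of the ENTR effect.

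**Hypothesis 3b and any SEM.** Use the same two indicators and the same named YRI contrast.

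**Hypothesis 3c.** Moderation is on the path from group to mediator, so each arm indicator needs its own W interaction. Use labels that do not clash with a1 and a3, for example g_YRI and g_C:
- MH(12 months) = B0 + a_YRI*X_YRI + a_C*X_C + d*W + g_YRI*X_YRI*W + g_C*X_C*W

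The YRI indirect effect is then (a_YRI + g_YRI*W)*b, and the YRI moderation test is on g_YRI.

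**Cost.** This changes SAP wording only: one more indicator per equation and, in 3c, one more interaction than the text already implies. No new data are needed. Some precision may be lost compared with a pooled contrast. With equal arms of size n, common SD s and no clustering, the variance of the mediator contrast is s²(1/n + 1/n) = 2s²/n against ENTR-only alone. Against both other arms pooled it is s²(1/n + 1/(2n)) = 1.5s²/n. The standard error is then larger by √(2/1.5) = 1.15, about 15%.
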